6. GENERAL ANALYSIS DEFINITIONS

6.1 TREATMENT(S)

In this Phase I trial, treatments are not randomized. In Parts A and B, different dose levels of BI 891065 alone (Part A) or of BI 891065 in combination with BI 754091 (Part B) are being administered. In the expansion part (Part C), patients will be treated with the dose combination that has been determined in Part B.

The data will be presented separately for each part, if not specified otherwise. All planned analyses will be presented by initial treatment group, i.e. in Parts A and B for all dose cohorts separately and in total over all dose cohorts of that trial part. Patients where treatment group assignment in terms of dose cohorts within a trial part has not been followed will be handled on a case-by-case basis and will be agreed upon latest at the report planning meeting before database lock of the specific trial part.

For safety summaries events that start from the first administration of any trial medication until 30 days (REP) after the last administration of any trial medication will be considered as having occurred “on-treatment”. If not specified otherwise, all safety tables will be based on the on-treatment period. Adverse events that have onset during the screening or the follow-up period will be displayed in separate listings from those that occurred during the on-treatment period. The MTD evaluation period will be defined as start of cycle 1 + 21 days for all patients. Labels of each analysing treatment period, analysis numbers, the labels used for displays in the tables and listings in the CTR, as well codes, decodes, sort order and labels for each trial medication are provided in the TSAP technical documents.

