- a Treatment cycles (C) are 21 days (3 weeks). Patients may continue treatment with BI 891065 and BI 754091 as long as they are deriving benefit according to the Investigator's judgment. All circumstances for withdrawal of trial treatment are presented in Section 3.3.4.1.
- b Screening should take place within 28 days of start of study treatment, however, may be extended as outlined in Section 6.2.1.1.
- c Safety laboratory assessments including haematology, serum biochemistry, coagulation, serum pregnancy test, and urinalysis will be performed locally. The following screening parameters should be done ≤ 14 days prior to initiation of treatment: medical history and demographics, physical examination (including height and weight), Eastern Cooperative Oncology Group (ECOG) performance status, vital signs, electrocardiogram (ECG), haematology (per Section 5.2.3), clinical chemistry (sodium, potassium, phosphate, chloride, creatinine, calcium, venous bicarbonate HCO_3 , albumin, total protein, aspartate aminotransferase [AST], alanine aminotransferase [ALT], alkaline phosphatase, total, direct and indirect bilirubin, lactate dehydrogenase, serum glucose, creatinine kinase [CK: if CK is elevated, then CK-MB, Troponin I/Troponin T, and myoglobin should be reactively tested, with further follow-up as clinically warranted], serum urea nitrogen, serum uric acid, and thyroid panel [TSH, free T4, and free T3]), urinalysis, and screening pregnancy test. If these assessments are performed within 72 hours of initiation of treatment, they do not need to be repeated on Cycle 1 Day 1 with the exception of the ECOG performance status, an abbreviated physical examination, vital signs, and single/triplicate ECGs as outlined in Section 5.2.4 and Table 10.3: 2 required prior to first administrations of trial treatments. Tumour assessments (scans) should be performed ≤ 28 days prior to initiation of treatment. Refer to Section 5.2.3 for additional details. Vital signs (blood pressure, body temperature, and pulse rate) are checked at every visit prior to blood work and trial treatment and at the discretion of the Investigator (see Section 5.2.2).

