2.1.2.2 Part B

The primary endpoints for Part B of the trial are the MTD of BI 891065 in combination with BI 754091 and the number of patients with DLTs during the first treatment cycle. Q.D. and b.i.d. dosing schedules may be explored in Part B. The MTD is defined as the highest dose combination with less than 25% risk of the true DLT rate being equal to or above 33%.

The primary endpoints of this part will be evaluated based on a timeframe from first treatment administration until the end of the MTD evaluation period (the end of the first cycle).

Another BLRM employing the EWOC principle will be used during the escalation phase for selection of dose combinations and for estimation of the MTD. It is planned that cohorts of patients will receive escalating doses of BI 891065 in combination with BI 754091 (at the dose pre-specified by the SRC) until the MTD is reached or the highest tolerated dose of BI 891065 determined in Part A has been tested. Each cohort will consist of newly enrolled patients. Estimation of the MTD during the combination escalation phase of the trial will be based upon the estimation of the probability of a DLT in Cycle 1 in the set of evaluable

patients for MTD. The corresponding methodology is described in Section 7 and in the statistical appendix (see Appendix 10.5). The MTD estimate established during the dose escalation of Part B will be re-investigated at the end of Part B by re-running the BLRM using the DLT information from all treatment cycles to determine the recommended dose combination for further development.

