4. TREATMENTS

4.1 INVESTIGATIONAL TREATMENTS

4.1.1 Identity of the Investigational Medicinal Products

Patients will receive either BI 891065 monotherapy or BI 891065 in combination with BI 754091 (see [Table 4.1.1: 1](#) and [Table 4.1.1: 2](#)).

Table 4.1.1: 1 BI 891065

Substance:	BI 891065
Pharmaceutical formulation:	Film-coated tablets
Source:	Boehringer Ingelheim Pharma GmbH & Co. KG
Unit strength:	5 mg, 20 mg, 50 mg, 100 mg tablets
Posology	Once daily (q.d.) or twice daily (b.i.d.), individual dose depending on dose escalation
Route of administration:	Oral

Table 4.1.1: 2 BI 754091

Substance:	BI 754091
Pharmaceutical formulation:	Solution for infusion after dilution
Source:	Boehringer Ingelheim Pharma GmbH & Co. KG
Unit strength:	20 mg/mL (vial with 15 mL filling volume)
Posology	Infusion on day 1 of 21-day cycles
Route of administration:	Intravenous infusion

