4.1.8 Definition of dose-limiting toxicity

Dose-limiting toxicities (DLTs) will be recorded throughout the trial. Any DLT must be reported to the [REDACTED] Medical Monitor by the Investigator or designee within 24 hours of first knowledge, and to the [REDACTED] as an SAE when appropriate. All DLTs will be agreed upon between the Sponsor, the Study Chair, the [REDACTED] Medical Monitor, and the Investigators after review of the data from each cohort. Only DLTs starting in the first cycle of monotherapy during Part A or during the first cycle of BI 891065 in combination with BI 754091 during Part B are necessary for dose-escalation decisions made by the SRC. DLT information from later cycles will be taken into consideration if available.

All relevant safety information (including DLTs) together with data on target engagement will be considered when selecting the recommended doses for the expansion cohorts.

Severity of AEs will be graded according to CTCAE Version 5.0. Any of the following AEs will be classified as DLTs following review by the Investigators and the [REDACTED] Medical Monitor unless unequivocally due to underlying malignancy or an extraneous cause.

Haematologic toxicities:

- For patients with solid tumours:
 - Any Grade 5 toxicity
 - Neutropenia \geq Grade 4 lasting for >5 days
 - Febrile neutropenia of any duration (ANC $<1.0 \times 10^9$ cells/L and fever $\geq 38.5^\circ\text{C}$)
 - Neutropenia Grade 3 with documented infection
 - Grade 4 thrombocytopenia, or Grade 3 thrombocytopenia with bleeding or a requirement for platelet transfusions
 - Grade 4 anaemia unexplained by underlying disease.

Non-haematological toxicities:

- AST or ALT >3 times ULN and concurrent total bilirubin >2 times ULN without initial findings of cholestasis (e.g., findings consistent with Hy's law or the FDA definition of potential DILI)
- \geq Grade 4 AST or ALT of any duration
- Any \geq Grade 3 non-haematologic toxicity with the following exceptions:
 - Grade 3 irAE that resolves to \leq Grade 1 or to baseline with immunosuppressive therapy within 2 weeks
 - Grade 3 fatigue that persists <7 days
 - Grade 3 rash that resolves to \leq Grade 1 within 2 weeks
 - Grade 3 or 4 elevation in serum amylase and/or lipase that is not associated with clinical or radiographic evidence of pancreatitis
 - Grade 3 electrolyte abnormality that lasts <72 hours, is not clinically complicated, and resolves spontaneously or responds to conventional medical intervention

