5.2.6.4.3 Cytokine release syndrome

Events of CRS CTCAE Version 5.0 Grade ≥ 2 are defined as AESIs. Patients will be closely monitored for CRS and, in case of suspected or confirmed CRS, appropriate treated according to best medical judgement based on institutional standards and/or publications (e.g., Lee et al. 2016 [R16-2323]). For the treatment of CRS, supportive therapy including steroids and / or interleukin 6 receptor (IL6R) antagonists (R15-0031) may be used as clinically indicated.

For Part A:

- Patients will remain under surveillance for 10 hours after first administration of BI 891065 [REDACTED]
- Patients will remain under surveillance for at least 8 hours after the second and third administrations of BI 891065.

For Part B:

- Patients will remain under surveillance after the administration of BI 891065 [REDACTED] in combination with BI 754091 [REDACTED] during Cycles 1 and 2.
- Duration of surveillance will be for 8 hours after the first dose of BI 891065 during Cycle 1, and for 6 hours after the first dose of BI 891065 in Cycle 2

For Part C:

- Patients will remain under surveillance after the administration of BI 891065 [REDACTED] in combination with BI 754091 [REDACTED] during Cycles 1 and 2.
- Duration of surveillance will be for 4 hours after the first dose of BI 891065 during Cycles 1 and 2.

Although patients will not be required to stay overnight on the first day of monotherapy or combination therapy treatments, they should be advised to remain close to the study site where medical coverage will be ready to support them, if required. Thereafter, patients will

be monitored with regular safety visits. All trial sites will have emergency resuscitation services and access to intensive care available.

Monitoring will include measurement of body temperature, heart rate, and blood pressure at regular intervals as presented in [Part A Flow Chart](#), [Part B Flow Chart](#), and [Part C Lung Flow Chart](#). Patients will be assessed for signs or symptoms of CRS (e.g., hypotension, hypoxia, tachycardia, fever, nausea, fatigue, headache, myalgias, and malaise).

Patients will be informed about possible signs and symptoms of CRS, and the need to immediately contact or present to the investigational site if symptoms occur after discharge.

The following recommendations for the management of CRS regarding administration of BI 754091 and BI 891065 should be considered by the Investigator as guidance:

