5. ENDPOINT(S)

5.1 PRIMARY ENDPOINT(S)

Part A:

The primary endpoints for Part A of the trial are the MTD of BI 891065 and the number of patients with dose-limiting toxicities (DLTs) during the MTD evaluation period (first treatment cycle). For definition of the MTD, refer to Section 2.1.2.1 of the CTP.

Part B:

The primary endpoints for Part B of the trial are the MTD of BI 891065 in combination with BI 754091 and the number of patients with DLTs during the MTD evaluation period (first treatment cycle). For definition of the MTD, refer to Section 2.1.2.2 of the CTP.

Part C:

The primary endpoint is OR by investigator's assessment based on RECIST version 1.1 (2). For definition of OR refer to CTP Sections 2.1.2.3.

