6.7 BASELINE, TIME WINDOWS AND CALCULATED VISITS

Study days and visits will be labelled according to the flowchart in the CTP.

Unless otherwise specified baseline is defined as the time point closest to but prior to the first administration of any study medication. If no time is specified and the date is the same as the first administration date, then it will still be considered baseline if not specified otherwise. If there is no measurement earlier than the first administration of study medication, then no baseline will be derived.

Laboratory values:

Baseline is defined as the latest time point before the very first administration of any study medication. For laboratories where not only the examination date but also time are recorded, examination time has to be taken into account when defining baseline. That is, a laboratory value on the same date as the first administration of study medication is considered as baseline value if and only if the time of laboratory assessment is before or the same as the time of first study drug administration.

If any of these times is missing and the date of laboratory assessment is equal to the date of first administration of study medication, then the laboratory assessment will be considered as according to protocol, i.e. as prior to first study medication.

Imaging time windows:

In order to identify whether consecutive imaging time points are missing for a given patient, a nominal time point (6, 12, ... weeks etc.) will be assigned to each and every image. This is achieved by creating windows for every radiological response assessment. These windows are defined in Table 6.7: 1.

Table 6.7: 1 Nominal time points and windows for imaging

Nominal time point (weeks from start of study medication)	Due date of scans (days)*	Window (days)
6	43	1 to ≤ 64
12	85	65 to ≤ 106
18	127	107 to ≤ 148
24	169	149 to ≤ 200
33	232	201 to ≤ 263
42	295	264 to ≤ 326
51	358	327 to ≤ 389
Etc., 9 week interval	Etc.	Etc.

* the date of the first dose of study medication is Day 1

If a patient does not have an image in one of the windows described above, he/she will be said to have missed an assessment for that time point.

ECG analysis:

Baseline values will be derived from the 1-3 triplicate ECG recordings prior to the first drug administration on Day 1 (refer to [Section 7.8.4](#)).

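### SAP 6.1 gives the MTD evaluation period no last day; under either reading, visit timing can let a DLT that starts after the second BI 754091 infusion into the Part B first-cycle count

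*SAP*

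**What the plan says.** SAP 6.1 fixes one calendar rule: "The MTD evaluation period will be defined as start of cycle 1 + 21 days for all patients". It does not say whether the last day is included, whether onset time is used, or what happens when Cycle 2 starts early or late. Period labels are left to technical documents that were not available for this review.

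Elsewhere the same period is treated as the first cycle:

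- SAP 5.1 names as a primary endpoint "the number of patients with DLTs during the MTD evaluation period (first treatment cycle".
- Protocol 2.1.2.2 runs the Part B endpoint "until the end of the MTD evaluation period (the end of the first cycle".
- Protocol 4.1.8 states which DLTs the escalation decisions need: "Only DLTs starting in the first cycle of monotherapy during Part A or during the first cycle" of the combination in Part B.

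On timing, the Part B flow chart footnotes say "Treatment cycles (C) are 21 days (3 weeks", and the chart gives Cycle 2 Day 1 a window of ±2 days. Protocol Table 4.1.1: 2 gives the BI 754091 schedule as "Infusion on day 1 of 21-day cycles".

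Under SAP 7.4 the Part B model is run once on first-cycle DLTs in the MTD evaluation set and once on all on-treatment DLTs in the treated set.

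**The concern.** The SAP uses a count of days and the protocol uses a cycle. The two differ at the boundary, and in Part B the boundary is an infusion day. The protocol itself expects acute reactions there: its cytokine release section requires surveillance in Cycle 1 "and for 6 hours after the first dose of BI 891065 in Cycle 2".

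If a DLT starts after that infusion, the drug given in Cycle 2 may have caused it. Whether it counts as a first-cycle event should not turn on whether the visit was held a day or two early. The first-cycle count is itself a primary endpoint and is the input to the primary BLRM run. With cohorts of five to eight evaluable patients, a single DLT matters. A second risk is that the reported count differs from the one the Safety Review Committee used under protocol 4.1.8.

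**Working it through.** **Day convention.** The only explicit day count in the SAP is the note to Table 6.7: 1, for imaging: "the date of the first dose of study medication is Day 1". So study day = 1 + elapsed days. For week w the due day is 7w + 1: 7 × 6 + 1 = 43, and weeks 12, 18, 24, 33, 42 and 51 give 85, 127, 169, 232, 295 and 358. All seven match the table.

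**Applied to SAP 6.1.** Start of Cycle 1 is Day 1, so start + 21 days is Day 22. A 21-day cycle covers Days 1 to 21, so Cycle 2 Day 1 is nominally Day 22. With ±2 days it may fall on Days 20 to 24.

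| Second infusion given on | Period ends Day 22 (inclusive) | Period ends Day 21 |
|---|---|---|
| Day 20 | inside | inside |
| Day 21 | inside | inside |
| Day 22 | inside | outside |
| Day 23 | outside | outside |
| Day 24 | outside | outside |

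Neither reading keeps Cycle 2 dosing out of the period for every permitted visit day.

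**What one extra DLT does, from the protocol alone.** Table 10.5: 11 gives the probability of overdose at the current dose:

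- 100/240, from 1/3 to 2/3 DLTs (Scenarios 2 and 3): 0.066 to 0.256.
- 200/240 after 0/3 at 100/240, from 1/3 to 2/3 DLTs (Scenarios 6 and 7): 0.117 to 0.308.

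Both cross the 0.25 limit.

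**What it does to the observed Part B data.** Inputs are the Table 7.1.2: 5 counts (0/6 at 50 mg, 0/8 at 200 mg and 1/5 at 400 mg, each with BI 754091 240 mg), the Table 10.5: 7 priors, and the five-parameter model of protocol 7.1.2. The model was rebuilt by importance sampling with 2 million prior draws. The BI 754091 reference dose d2* was set in turn to 240 mg and to the 3200 mg written in 7.1.2.

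Check against the plan's own figures: Table 7.1.2: 6 gives 0.615 / 0.313 / 0.072 for under-, target and overdosing at 400 mg q.d. With d2* = 240 mg the rebuilt model gives 0.614 / 0.314 / 0.073, and the mean is 0.154 in both. The lower-dose rows agree less closely: at 200 mg q.d. the mean is 0.102 against 0.110 stated. That is a reminder that the table may rest on an updated prior. With d2* = 3200 mg the overdose probability at 400 mg is about 0.039, which does not match 0.072.

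| DLTs at 400/240 | P(overdose), d2* = 240 mg | P(overdose), d2* = 3200 mg |
|---|---|---|
| 1/5 | 0.073 | about 0.039 |
| 2/5 | 0.259 | 0.149 |

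With d2* = 240 mg the excess over the limit is 0.259 − 0.25 = 0.009.

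**The case against.** The strongest reply is that start plus 21 days is simply a 21-day span, Days 1 to 21. That fits the cycle length, the SAP's own label for the period, the three-week first cycle in protocol 2.1.3 (written for PK endpoints), the three-week observation in 4.1.3.1, and the 21-day observation period in the Part B biopsy footnote. A fixed window also gives every patient the same observation time, which suits a binomial likelihood. This reading is plausible and removes the Day 22 case. It does not remove the Day 20 and Day 21 cases.

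A reader might infer that the SAP makes acute reactions to the second infusion count as first-cycle DLTs. The documents do not say that. An event must meet the DLT criteria and be agreed by the sponsor, study chair, medical monitor and investigators. Protocol 4.1.8 also has time to onset weighed when deciding whether a toxicity is a DLT for escalation. These safeguards make misclassification less likely, but they are not a derivation rule for the reported count.

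The consequence is also bounded. Later-cycle DLTs are considered when available, the model is rerun on all on-treatment DLTs, and the Safety Review Committee, not the model alone, sets the MTD. The infusion argument concerns Part B only: Part A is oral monotherapy and SAP 4 records that Part C was cancelled. All of this stands, and it makes the point a limited one.

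**Conclusion.** The SAP's calendar rule and the protocol's first-cycle endpoint do not coincide. The end day is undefined, and under both natural readings a Part B DLT with onset after the second infusion can enter the first-cycle count because of when the visit was held. This follows from the date arithmetic and the ±2-day window, and needs no modelling assumption.

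The size is hypothetical. The documents report no such event, and Table 7.1.2: 5 shows 1 DLT in 6 + 8 + 5 = 19 evaluable Part B patients. One extra DLT at 400/240 would give a probability of overdose of about 0.26 with d2* = 240 mg or about 0.15 with 3200 mg, assuming the Table 10.5: 7 priors. A reader might infer that 400/240 would then fail EWOC. The documents do not support that as a firm conclusion: with the stated reference dose it would still pass, and with 240 mg it would fail by only 0.009. What stands is that a single reclassified DLT can matter in cohorts this small, as Table 10.5: 11 also shows. It is worth correcting in the SAP, but it is not evidence that any reported count is wrong.

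**What to change.** In SAP 6.1, replace the sentence with a rule along these lines:

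1. The MTD evaluation period runs from Day 1 (date of first dose) to Day 21 inclusive, and DLTs are assigned by onset.
2. If the first Cycle 2 administration of any trial drug falls on or before Day 21, DLTs with onset after it go to the all-cycle analysis and not to the first-cycle count.
3. If onset is on that dosing date and no time is recorded, the documented DLT review assigns the cycle, and the table carries a footnote.
4. Toxicity with onset in Cycle 1 that prevents Cycle 2 Day 1 dosing stays in the first-cycle count.

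Item 3 is needed because protocol 8.3.1 lists the adverse event onset date as mandatory and mentions no time. The cost is a short SAP edit, one derivation rule and, for the rare untimed event, a line in the DLT review record. The downside is small: patients who start Cycle 2 on Day 20 or 21 have a slightly shorter window than the rest.

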6.2 IMPORTANT PROTOCOL DEVIATIONS

No per protocol set analysis will be performed for this study, hence no patient will be excluded from this analysis. However, patients with important protocol deviations (IPDs) will be documented. The following table defines the different categories of IPDs. The final list of IPDs will be confirmed at the last report planning meeting before database lock for the analysis.

Table 6.2: 1 Important protocol deviations

Category / Code	Description	Comment / Example	Excluded from	Automatic / Manual
A	Entrance criteria not met			
A1	Patient has condition that may cause additional risk from study medication	IN3; EX7, EX8, EX9, EX10, EX12, EX13, EX16, EX17	None	Automatic

Table 6.2: 1 Important protocol deviations (cont.)

Category / Code	Description	Comment / Example	Excluded from	Automatic / Manual
A2	Patient has laboratory assessment that may cause additional risk	EX11, EX21	None	Automatic
A3	Patient is unable to comply with the protocol	EX3, EX15	None	Automatic
A4	Patient does not have trial diagnosis or is not part of the target population	IN2, IN4, IN5, IN6, IN7, IN8, IN9 EX20, EX22, EX23, EX24	None	Automatic
A5	Patient has condition that may interfere with evaluation of safety and/or efficacy	EX1, EX2, EX4, EX5, EX6, EX14, EX18, EX19	None	Automatic
B	Informed consent			
B1	Trial Informed consent not available, not done	IN1	All	Automatic
B2	Informed consent too late	Date of informed consent later than the first study related procedure (This does not include the informed consent for biobanking and the informed consent for treatment beyond progression)	None	Automatic

Table 6.2: 1 Important protocol deviations (cont.)

Category / Code	Description	Comment / Example	Excluded from	Automatic / Manual
B3	Informed consent for treatment beyond progression not available or too late	Date of informed consent for treatment beyond progression not available although patient treated after progression or date of informed consent for treatment beyond progression later than first administration of trial medication after progression	None (as long as patient has not withdrawn from the general study informed consent)	Automatic
C	Trial medication			
C1	Incorrect treatment taken	
 Study medication dispensing error leading to change in actual treatment 	None	Manual
C2	Incorrect dose administered	E.g. reduction criteria as specified in CTP Section 4.1.7 met but no dose reduction	None	Manual
C3	Discontinuation of study medication not according to protocol	Discontinuation criteria as specified in CTP Section 4.1.7 met but study medication not discontinued	None	Manual
D	Concomitant medication			
D1	Prohibited medication	
 Immunosuppressive medications Live attenuated vaccines Herbal preparations / medications 	None	Automatic & Manual

Table 6.2: 1 Important protocol deviations (cont.)

Category / Code		Description	Comment / Example	Excluded from	Automatic / Manual
E		Trial specific violations			
	E1	Pregnancy test not done	Pregnancy test not done in women of childbearing potential although indicated by the protocol	None	Automatic & Manual

